4. AIMS / OBJECTIVES / HYPOTHESES

Our goal is to address three types of adversities that hinder women’s empowerment and early child development in low- and middle-income countries: low take-up of healthcare and other social safety net programs (including cash- and food-transfers), lack of knowledge about the importance of the early years on future child development and long-run outcomes, and psychological constraints associated with maternal depression. We aim to test to what extent these three interventions offer practical opportunities to improve maternal health, birth, and child development outcomes in cost-effective ways. We believe that these interventions might be even more effective than previous similar interventions because we will be targeting women

early in pregnancy (and in some cases even prior to conception), which is considerably earlier than most previous studies aimed at improving maternal and child outcomes.

Our specific **objectives** are:

- 1) Explore what are pregnant women’s views about the idea of a “healthy pregnancy” and how these perceptions translate to actual health behaviours and investments in children.
- 2) Investigate if providing the three following targeted interventions to women early in pregnancy offers cost-effective ways to enhance maternal wellbeing and children’s physical and mental development:
 - a. Information about women’s eligibility to health services and other safety net programs and assist them with the enrolment process.
 - b. Information to pregnant mothers and their families on the importance of the early-life environment, and especially the 9-month in utero period, in laying the foundations for a child’s lifelong success.
 - c. Psychological counselling to pregnant women starting early in pregnancy.

Our study has four main **hypotheses**, each of which will be tested by a different intervention:

- 1) According to government data, programs aimed for women with children are often undersubscribed, which may be largely explained by the fact that many poor women are not aware of the existence of these programs, their potential eligibility, or how to navigate the system to get enrolled. In fact, among the relatively few mothers that do get enrolled, they are often enrolled too late into (or even after) their pregnancy, missing critical windows for fetal development. Given this, we hypothesize that providing information on government programs and enrolment support will improve program take-up and women and children’s outcomes.
- 2) While knowledge on the signature importance of the “fetal origins” and early childhood periods (Barker, 1990, Almond and Currie 2011) is widespread among clinicians and social scientists, the full range of effects may be less known to disadvantaged groups such as women in remote areas in low- and middle-income countries. Thus, to the extent that expectant mothers’ beliefs underestimate the returns of prenatal investments on children’s future outcomes, or misperceive the malleability of fetal health, we hypothesize that interventions that target maternal beliefs starting in early in pregnancy will be effective at promoting children’s future potentials.
- 3) Research has shown that while psychological interventions conferred substantial benefit to mothers, they have not been effective in improving outcomes for children (Baranov et al. 2020, Angelucci and Bennett 2021). A likely cause is that interventions typically start too late (in the third trimester of pregnancy), and we hypothesize that a early start of psychological interventions will result in substantial benefits to mothers’ and children’s outcomes.
- 4) In low-income settings agents are often faced with numerous challenges that may interact in ways that prevent information or psychological interventions alone from generating significant or sustained improvements, and even more so to other agents within the household. Indeed, recent work suggests that poverty and low psychological

well-being mutually reinforce each other in a vicious cycle (Ridley et al. 2020). We hypothesize that relaxing multiple constraints, namely through information provision, economic transfers (cash, food, services), and psychological counselling will be complementary, reinforcing each other (Haushofer et al. 2020, Angelucci and Bennett 2021)

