
POPULATION
	
Our population includes newly married women, pregnant women, and mothers with young children aged 6 months or younger located in two subdistricts of Gazipur district in Bangladesh. According to the Demography and Health Surveys of 2014, women in Bangladesh tend to marry early. By age 18, 50% are married and their first child arrives 1.5 years later, which means that many women become mothers as teens. Moreover, 98.6% get married and nearly all have at least one child. As a result, there is virtually no selection into fertility in this setting. Two thirds of women deliver their child at home, have between one and two antenatal visits. Half have primary education or less, and less than 35% work outside home (half of which are employed in agriculture). Husbands are on average 10 years older, have similar levels of education, and the vast majority work in agriculture or in the informal sector. Moreover, Bangladesh has one of the highest rates of malnutrition in the world. 20% of children born in the country every year are born either “small” or “very small” (Demography and Health Survey, DHS 2014), 41% of those below the age of 5 are stunted, and about five million children are out of school (World Bank, 2015).

SELECTION AND ENROLMENT
	
Eligibility criteria for inclusion:
 
 1. Listed in the digital database of Kapasia Model 2. Permanent residence of any of the two subdistricts of Gazipur district in Bangladesh 3. Newly married women 4. Pregnant women 5. Mothers with young children aged 6 months or younger 
To be eligible, women must fulfill the first and the second criteria, any of the criteria from 3 to 5 must be fulfilled.

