To evaluate the impact of these three interventions, we will conduct a 3x2 factorial RCT across two sub-districts in rural Bangladesh. The two information treatments will be cross randomized with the one mental health intervention. The mental health intervention will be randomized at the Union Health and Family Welfare Centre (UHFWC) level (there are 20 total UHFWCs across the 2 Upazilas), stratified by sub-district, and allocated at a 1:1 ratio. We will then randomly select 120 villages within subdistricts, stratified by UHFWC, to participate. The information interventions will be randomized at the village level, stratified by UHFWC, with 40 villages receiving information and enrolment support for government programs, 40 villages receiving additional information on the importance of early life conditions, and 40 control (no information) villages. Eligible participants will be pregnant women and mothers with young children aged 6 months or younger. We will aim to recruit 22 women per village to be part of the study sample.

We will use two types of data, (i) the data from the digital information system of Kapsasia Model built at the sub-district level by the local government, which we call *administrative data*, and (ii) household and individual survey data including elicitation of maternal beliefs of prospective and existing mothers that we will collect as a part of the study, which we call *household survey data*. This survey will be conducted on the sample of 22 women per village for a **total sample of 2,640 women**. The administrative data include information (e.g., age, education, occupation, mobile phone number, pregnancy status, birth outcomes, number of children) on *all* registered newly married couples in our study area, including the 22 women per village in our study sample, and will identify key outcomes such as pregnancy status and birth outcomes. We will conduct a baseline survey with an endline 10 months later, and we plan to conduct a midline survey by phone (which will likely be funded using internal funds² from the University of Sydney and University of Melbourne) to measure parental inputs in the in utero period. The schedule of enrolment, intervention and evaluations is given in Figure 1.

² They have not been mentioned in the budget as no firm commitment has been received yet.

The study schedule	Study period													
	Baseline							Midline				Endline		

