	1st month	2nd month	3rd month	4th month	5th month	6th month	7th month	8th month	9th month	10th month	11th month	12th month	13th month	14th month
Enrolment														
Eligibility Screening	X													
Consent collections		X												
Randomization & allocation to treatments and control group			X											
Interventions/ Treatments														
1. Information and enrolment support to govt. programs				X	X	X	X	X	X	X	X			
2. 1 + Information on the importance of early life conditions				X	X	X	X	X	X	X	X			
3. Psychological counselling				X	X	X	X	X	X	X	X			
Evaluations														
Compliance Check - if individuals and groups assigned to treatments and controls are in fact complying to the assignment					X	X	X	X	X	X	X			
Household characteristics and other basic information, houses, lands, and asset ownership, economic activities and employment, beliefs, women mental health, preferences		X										X		
Parents time and monetary investment on children								X						
Anthropometry & health, children’s mental health and development, take up of health care services, participation in social transfers/safety net programs, parenting style, parents time and monetary investment on children, food intake/share, food insecurity & non-food expenditures, women empowerment, intimate partner violence													X	
Data Analysis														X X
Report Writing/ Publication														X X

Figure – 1: Schedule of enrolment, intervention, and evaluations

Power Calculation: Given the sample sizes above and accounting for the varied clustered design, we would be powered to detect a Minimum Detectable Effect (MDE) size of 0.31 of a standard deviation (SD) change for the mental health intervention (randomized at the Health Centre (UHFWC) level with the conservative estimate of 20 centers). For the information arms, we would be powered to detect a 0.19SD change for either of the information interventions (main effects only). As benchmark for the MDEs on mental health interventions, Rahman et al. (2008) found that a mental health intervention similar to the one proposed here improved mothers’ mental health by 0.70SD, while Sikander et al. (2019) found that a more scalable, peer-delivered version of the intervention increased mothers’ mental health by 0.30SD. A tele-counseling intervention in Bangladesh improved mental health by 0.65SD (Vlassopolous et al. (2021)).

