11. TIMELINES / MILESTONES

An approximate study timeline is provided in Figure 2. We plan to complete the study within 14 months from start. In the first month, the eligibility criteria of participants which will be selected from the Kapasia Model digital database, will be re-checked, and informed consents of the eligible participants will be sought. This will be followed by commencement of the baseline survey in the second month of the study, and the random allocation of participants to different treatments will be achieved in the third month. The list of participants that will receive psychological counselling will be given to the relevant implementing partner Moner Bondu,

and the rest of interventions will be carried out by the research team. In the fifth month, compliance to treatments and control status will be checked followed by a midline telephone survey in the eighth month. We will conduct the endline survey after 10 months of the intervention followed by data analysis and report writing / manuscript preparation.

[figure not shown]

Figure 2: Study Timeline

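### The eligibility rules and calendar do not deliver the claimed early-pregnancy or pre-conception exposure for most of the sample, and the protocol contradicts itself on who is eligible and when endline falls

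*Protocol*

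**What the plan says.** **Claim.** Section 4 says that women will be reached "early in pregnancy (and in some cases even prior to conception), which is considerably earlier than most previous studies". Hypothesis 3 attributes earlier null results in children to interventions that began in the third trimester. Hypothesis 2 also assumes an early start. No gestational age is given for what counts as early.

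**Calendar.** Section 11: "In the first month, the eligibility criteria of participants which will be selected from the Kapasia Model digital database, will be re-checked"; then "commencement of the baseline survey in the second month of the study"; then "the random allocation of participants to different treatments will be achieved in the third month". Figure 1 ("Schedule of enrolment, intervention, and evaluations") marks all three interventions in months 4 to 11, an endline survey in month 12, and anthropometry and child development in month 13. The whole study is to finish within 14 months.

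**Endline.** Section 6: "We will conduct a baseline survey with an endline 10 months later". Section 11: "We will conduct the endline survey after 10 months of the intervention".

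**Eligibility.** The Synopsis lists newly married women, pregnant women and mothers of infants up to 6 months as criteria 3 to 5, and says that "any of the criteria from 3 to 5 must be fulfilled". Section 6 names only pregnant women and mothers of infants up to 6 months. Neither sets an upper limit on gestation, and neither gives the expected mix of the three groups.

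**The concern.** Gestation at first exposure is what is meant to separate this trial from earlier ones. Three months pass between the start of screening and the start of the interventions, and entry is open to any stage of pregnancy and to women who have already delivered. Women reached before conception need about nine further months before there is a child to measure, and endline comes about nine months after the interventions begin. The only group that could supply first-trimester exposure together with a birth by endline is included in one section and left out of another.

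What is at stake is the meaning of the child results. If most measured children were first exposed in the third trimester or after birth, a pooled estimate describes the very timing that hypothesis 3 blames for earlier failures, not the early start that the protocol sets out to test.

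**Working it through.** **Conventions.** Month k runs from time k-1 to k, so month 4 starts at t = 3.0. One month is 30.4375 days, or 4.348 weeks.

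**Assumptions not in the protocol.** Conception to birth takes 266 days (266/30.4375 = 8.74 months). The first trimester ends at 14 weeks, the second at 28, and birth is at 40. Pregnancy becomes known at d = 4 to 8 weeks. Gestation is uniform from d to 40 weeks among women pregnant at screening.

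**1. Endline date.** Baseline in month 2 plus 10 gives month 12, which agrees with Section 6 and Figure 1. A month-4 start plus 10 gives about month 14, which is the Section 11 wording. Figure 1 shows 11 - 4 + 1 = 8 intervention months. The Section 11 wording therefore does not fit.

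**2. Women pregnant at screening.** From mid-month 1 to the start or middle of month 4 the lag L is 2.5 to 3.0 months (10.87 to 13.04 weeks). With g the gestation at screening:

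- second trimester at start: (28 - L - d)/(40 - d)
- third trimester: 12/(40 - d)
- already delivered: L/(40 - d)

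| d (weeks) | L (months) | First | Second | Third | Delivered |
|---|---|---|---|---|---|
| 4 | 2.5 | 0% | (28 - 10.87 - 4)/36 = 36.5% | 12/36 = 33.3% | 10.87/36 = 30.2% |
| 8 | 3.0 | 0% | (28 - 13.04 - 8)/32 = 21.7% | 12/32 = 37.5% | 13.04/32 = 40.8% |

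The third-trimester and delivered shares together are 63.5% to 78.3%. The first-trimester share is about zero rather than exactly zero. A woman at 4 weeks at the very end of month 1 would be at 4 + 2 x 4.348 = 12.7 weeks at the start of month 4. Month 4 is the best case, because delivery continues to month 11.

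**3. Mothers enrolled with an infant.** That child has no in-utero exposure.

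**4. Newly married women who conceive after the start.** The earliest birth is at 3.0 + 8.74 = 11.74, the last week or so of month 12. A birth by the end of month 13 needs conception by 13.0 - 8.74 = 4.26, that is, within the first 1.26 months. Such infants would be at most about 1.3 months old at the end of month 13.

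For the conception rate, the Synopsis puts the first birth 1.5 years after marriage: 18 - 8.74 = 9.3 months to conception, and 1/9.3 is about 11% per month. I take 5-20% as the range. For women not pregnant at t = 0.5, the share conceiving between t = 3.0 and 4.26 is (1-h)^2.5 - (1-h)^3.76:

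- h = 0.11: 0.747 - 0.645 = 10%
- h = 0.05: 0.880 - 0.825 = 5.5%, about 6%
- h = 0.20: 0.572 - 0.432 = 14%

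**5. Newly married women who conceive between screening and month 4.** The share is 1 - (1-h)^2.5: 25% at h = 0.11, 12% at 0.05 and 43% at 0.20. They are in the first trimester at the start and deliver by t = 11.74.

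**6. Across groups.** At the central rate, 25% + 10% = 35% of newly married women not pregnant at screening have an early-exposed child by the end of month 13, and the other 65% have no child to measure. Among women pregnant at screening, 22-37% start before the third trimester. Among mothers of infants, none do for that child. In each group most women lack the stated exposure. At h = 0.20 the newly married figure would be 43% + 14% = 57%, and the statement would then depend on the mix.

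**The case against.** A reader might infer that the trial has no first-trimester exposure at all. The documents do not support that. Under the Synopsis, newly married women who conceive between screening and month 4 have it and deliver before the end of month 12. Whether they are in the trial is what the two eligibility texts leave open.

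A reader might also infer that early effects on children cannot be shown. That too goes beyond the text. The protocol's contrast is with third-trimester starts, and no section promises a first-trimester start. Of women still pregnant at the start, 36.5/(36.5 + 33.3) = 52% down to 21.7/(21.7 + 37.5) = 37% are before the third trimester. The contrast is diluted but can be estimated.

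Other points stand in part:

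- The shares rest on assumed uniform gestation. The protocol does not say how the 22 women per village are drawn from the database, so a draw favouring recent pregnancies would improve them.
- The primary outcomes are maternal and child outcomes are secondary. Programme take-up under hypothesis 1 and the maternal results do not depend on first-trimester exposure.
- Subgroup specification is ordinarily left to an analysis plan. Eligibility, endline and the meaning of early are not, since they decide who enters and what is claimed.
- The final month columns of Figure 1 should be checked against the typeset table. Figure 2, the timeline, was not available.

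**Conclusion.** The concern holds in this form: the eligibility and calendar, as written, do not give the stated exposure to most of the sample. Under Section 6 eligibility there is no pre-conception group, first-trimester exposure is close to nil, and a pooled child result would mostly reflect third-trimester or post-delivery starts (63-78% of women pregnant at screening, plus every mother enrolled with an infant). Under the Synopsis eligibility this still holds unless newly married women form a large part of the sample, and the protocol does not give that share.

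The two contradictions, on newly married women and on endline, rest on the text alone. The calendar limits rest on the stated months and a 266-day interval from conception to birth. The percentages rest on uniform gestation, recognition at 4-8 weeks and monthly conception of 5-20%, and should be read as ranges. How readers would interpret a null result is a matter of judgement. The protocol establishes only that the pooled estimate would not isolate an early start.

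**What to change.** 1. Reconcile the Synopsis and Section 6 on whether newly married women are eligible, before enrolment begins.
2. Reconcile the endline date across Section 6 (10 months after baseline, month 12), Section 11 (after 10 months of the intervention, about month 14) and Figure 1 (eight intervention months, endline in months 12-13).
3. For the child outcomes under hypotheses 2 and 3, define the index child. Compute gestation at the scheduled intervention start from pre-randomisation data, in the same way in all arms, with women not known to be pregnant in those data as a separate category. Base conclusions about an early start on women pregnant and before the third trimester at that date. Report conceptions after randomisation separately and descriptively. Otherwise restate the claim as exposure during pregnancy.

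Extending follow-up until every pregnancy begun by month 11 has ended is not a good substitute. It would run to 11.0 + 8.74 = 19.74, about month 20. As the protocol describes the administrative data, it would add birth outcomes but not child development or growth. It would also bring in conceptions after randomisation, when agency in fertility planning is itself a primary outcome.

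The cost is wording and an earlier decision on eligibility, with no added fieldwork. The downside is lower precision in the early-start stratum and a narrower claim. Women who conceive shortly before allocation and are not yet known to be pregnant also fall outside that stratum.

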5. PARTICIPATING SITES

Our main participating sites are two sub-districts of Gazipur district of Bangladesh. One of the sub-districts will be Kapasia, while the other is yet to be selected. In each sub-district there are about 10 Union Health and Family Welfare Centre (UHFWC). We will randomly select 120 villages within two subdistricts, stratified by UHFWC, to participate.

6. RESEARCH PLAN / STUDY DESIGN

Our study is comprised of three treatments. In treatment 1, project officers employed by the research team, who will be located in study area, will provide information over the phone to each treated household on their eligibility (yes or no) of government's cash and food transfer programs, as well as where and how to enrol, and assistance with enrolment for eligible mothers.

Treatment 2 involves providing information to pregnant mothers and their families on the importance of the early-life environment, and especially the 9-month in utero period, in laying the foundations for a child's lifelong success. Eligible and willing participants who would be randomly assigned to receive this treatment will be contacted by our project officers, and the officer will provide the following information over the phone:

“A healthy pregnancy, wherein mothers take care of themselves and their children during their pregnancy, is extremely important for their children health and economic outcomes. Starting from as early as the 9th week of pregnancy, mothers who eat nutritious food and think positively give birth to healthier children who grow up to be healthier adults. A healthy diet during pregnancy such as this one, (this is based on study conducted in a similar setting, see: <https://bmjopen.bmj.com/content/bmjopen/7/8/e015393.full.pdf>)

Meal	Food	Quantity (one dish=250mL)
Breakfast	Rice	1.5 dishes
	or	
	Chapati (medium size)	3 pieces
	Vegetables	1 dish
	Egg	1
Mid-morning snack	Lentil (thick)	1 dish
	or	
Lunch	Seasonal fruit(s)	1 piece/dish
	Milk product(s)	1 dish
Afternoon snack	Rice	3 dishes
	Lentil (thick)	1 dish
	Leafy/non-leafy vegetables	1.5 dishes
	Meat/fish/egg	1 piece
Dinner	Milk	1 glass
	Seasonal fruit(s)	1 piece/dish
	Puffed rice with molasses or Biscuits	1 dish
Dinner	Rice	2 dishes
	Lentil (thick)	1 dish
	Leafy/non-leafy vegetables	1.5 dishes
	Meat/fish/egg	1 piece
	Milk or Curd	1 glass / 0.5 dish

	উপাদান	পরিমাণ
সকালের নাস্তা	ভাত	১½ বাটি (২৫০ মি.লি.+১২৫ মি.লি.)
	অথবা	অথবা
	অটার কুটি	৩টি (মাঝারি)
	সবজি ভাজি	১ বাটি (২৫০ মি.লি.)
	ডিম ভাজি	১টি
মাঝারি নাস্তা (সকাল ১০-১১)	যে কোন মৌসুমি ফল (মেম্বন-কলা/আম/কঁচালা/পেয়ারা/পেঁপে ইত্যাদি)	১টি (মাঝারি)
	অথবা	অথবা
দুপুরের খাবার	ভাত	৩ বাটি (২৫০ মি.লি.+২৫০ মি.লি.+২৫০ মি.লি.)
	মন ডাল	১ বাটি (২৫০ মি.লি.)
	শাক-সবজি	১ বাটি (২৫০ মি.লি.)
	মাছ/মাংস/ডিম	১ টুকরা (মাঝারি)
বিকালের নাস্তা	মুগ	১ গ্রাস
	অথবা	অথবা
সন্ধ্যার খাবার	দুধের তৈরী পায়েস/ফিরনি/পিঠা	½ বাটি (১২৫ মি.লি.)
	ভাত	২ বাটি (২৫০ মি.লি.+২৫০ মি.লি.)
	মন ডাল	১ বাটি (২৫০ মি.লি.)
	শাক-সবজি	১½ বাটি (২৫০ মি.লি.+১২৫ মি.লি.)
	মাছ/মাংস/ডিম	১ টুকরা (মাঝারি)

Figure 3 Five-meal menu for pregnant woman (Bengali).

can protect a child against low birth weight and stunting (short height) in infancy, and psychological problems, and diabetes or hypertension in adulthood. In contrast, children of mothers who suffer from long periods of stress during pregnancy can develop future health problems when they become adults themselves. Therefore, taking nutritious food regularly, managing stress, and thinking positively from the earliest stages of pregnancy are important for the child in the near- as well as in the long-term. It’s never too early to incorporate these positive changes to your routine.”

The third intervention involves offering psychological counselling based on Cognitive Behavioural Therapy, which will be provided by trained counsellors from Moner Bondhu (<https://www.monerbondhu.org/>). The content will follow the WHO-adopted and evidence-based programme called Thinking Healthy, specifically focusing on only the early (pre-delivery) sessions. Thinking Healthy has already been translated and adapted to Bengali (with the full manual for the management of perinatal depression available for free from the WHO website here: <https://apps.who.int/iris/bitstream/handle/10665/152936/WHO-MSD-MER-15.1-ben.pdf?ua=1&ua=1>). Eligible and willing participants who would be randomly assigned to receive this treatment will be contacted by an officer from Moner Bondhu. Participants will be invited to take part in 4 group counselling sessions, each lasting approximately 1-1.5 hours. The group will consist of other pregnant women from the same village enrolled in this study. We anticipate the groups will be approximately 22 women or less. Counsellors from Moner Bondhu will identify an appropriate venue with comfortable furnishing and privacy to hold the sessions. The sessions will use narratives, or stories, to engage women and then open the floor to discussion on the issues of (1) mother’s physical health, (2) coping with stress, (3) and mother’s relationship with the people around her. They will be modelled after the THPP

intervention (specifically see Chapter 2 in the THPP Manual). However, we will adapt the sessions to include a focus on identifying and coping with stressors.

To evaluate the impact of these three interventions, we will conduct a 3x2 factorial RCT across two sub-districts in rural Bangladesh. The two information treatments will be cross randomized with the one mental health intervention. The mental health intervention will be randomized at the Union Health and Family Welfare Centre (UHFWC) level (there are 20 total UHFWCs across the 2 Upazilas), stratified by sub-district, and allocated at a 1:1 ratio. We will then randomly select 120 villages within subdistricts, stratified by UHFWC, to participate. The information interventions will be randomized at the village level, stratified by UHFWC, with 40 villages receiving information and enrolment support for government programs, 40 villages receiving additional information on the importance of early life conditions, and 40 control (no information) villages. Eligible participants will be pregnant women and mothers with young children aged 6 months or younger. We will aim to recruit 22 women per village to be part of the study sample.

We will use two types of data, (i) the data from the digital information system of Kapsasia Model built at the sub-district level by the local government, which we call *administrative data*, and (ii) household and individual survey data including elicitation of maternal beliefs of prospective and existing mothers that we will collect as a part of the study, which we call *household survey data*. This survey will be conducted on the sample of 22 women per village for a **total sample of 2,640 women**. The administrative data include information (e.g., age, education, occupation, mobile phone number, pregnancy status, birth outcomes, number of children) on *all* registered newly married couples in our study area, including the 22 women per village in our study sample, and will identify key outcomes such as pregnancy status and birth outcomes. We will conduct a baseline survey with an endline 10 months later, and we plan to conduct a midline survey by phone (which will likely be funded using internal funds² from the University of Sydney and University of Melbourne) to measure parental inputs in the in utero period. The schedule of enrolment, intervention and evaluations is given in Figure 1.

² They have not been mentioned in the budget as no firm commitment has been received yet.

The study schedule	Study period													
	Baseline							Midline				Endline		
	1st month	2nd month	3rd month	4th month	5th month	6th month	7th month	8th month	9th month	10th month	11th month	12th month	13th month	14th month
Enrolment														
Eligibility Screening	X													
Consent collections		X												
Randomization & allocation to treatments and control group			X											
Interventions/ Treatments														
1. Information and enrolment support to govt. programs				X	X	X	X	X	X	X	X			
2. 1 + Information on the importance of early life conditions				X	X	X	X	X	X	X	X			
3. Psychological counselling				X	X	X	X	X	X	X	X			
Evaluations														
Compliance Check - if individuals and groups assigned to treatments and controls are in fact complying to the assignment					X	X	X	X	X	X	X			
Household characteristics and other basic information, houses, lands, and asset ownership, economic activities and employment, beliefs, women mental health, preferences		X										X		
Parents time and monetary investment on children								X						
Anthropometry & health, children’s mental health and development, take up of health care services, participation in social transfers/safety net programs, parenting style, parents time and monetary investment on children, food intake/share, food insecurity & non-food expenditures, women empowerment, intimate partner violence													X	
Data Analysis														X X
Report Writing/ Publication														X X

Figure – 1: Schedule of enrolment, intervention, and evaluations

Power Calculation: Given the sample sizes above and accounting for the varied clustered design, we would be powered to detect a Minimum Detectable Effect (MDE) size of 0.31 of a standard deviation (SD) change for the mental health intervention (randomized at the Health Centre (UHFWC) level with the conservative estimate of 20 centers). For the information arms, we would be powered to detect a 0.19SD change for either of the information interventions (main effects only). As benchmark for the MDEs on mental health interventions, Rahman et al. (2008) found that a mental health intervention similar to the one proposed here improved mothers’ mental health by 0.70SD, while Sikander et al. (2019) found that a more scalable, peer-delivered version of the intervention increased mothers’ mental health by 0.30SD. A tele-counseling intervention in Bangladesh improved mental health by 0.65SD (Vlassopolous et al. (2021)).

